16.4 Protocol Amendments

All protocol amendments (including consent form changes) must be initiated by the Protocol Chair and approved by the IRB prior to implementation. The FDA will be notified as required under 21 CFR 312.30. IRB approval is not required for protocol changes that occur to protect the safety of a subject from an immediate hazard. However, the Principal Investigator must inform the IRB, the Protocol Chair and the sponsor as described in 16.1.

16.5 Records Retention

The Principal Investigator will maintain study-related records for the longer of a period of:

- at least two years after the date on which a New Drug Application is approved by the FDA;
- at least two years after formal withdrawal of the IND associated with this protocol; or
- in compliance with local record retention policies.

16.6 Conflict of Interest

The Principal Investigator and Sub-Investigators must comply with applicable federal, state, and local regulations regarding reporting and disclosure of conflict of interest. Conflicts of interest may arise from situations in which financial or other personal considerations have the potential to compromise or bias professional judgment and objectivity. Conflicts of interest include but are not limited to royalty or consulting fees, speaking honoraria, advisory board appointments, publicly-traded or privately-held equities, stock options, intellectual property, and gifts. Investigators and key personnel must provide financial disclosures prior to trial participation and as interests change and complete any applicable institutional conflict of interest documentation per local policy.

18 APPENDICES

18.1 Appendix A: Radiation Therapy

The total targeted RT dose will be at the discretion of the treating Radiation Oncologist. Optimally, one treatment of 1.8-2.0 Gy/fraction will be given daily 5 days per week for a total targeted dose of 59.4-60.0 Gy over \leq 7 weeks. 3D conformal and intensity-modulated RT is permitted. All portals should be treated during each treatment session. Doses are specified as the target dose that shall be to the center of the target volume.

The gross target volume (GTV) for both the initial volume (GTV1) and the conedown volume (GTV2) should be based on the postoperative CT/MRI (and preferably the MRI; the preoperative scans may be used if postoperative scans are not available). This initial target volume (GTV1) should include the contrast-enhancing lesion (and should include the surgical resection cavity) and surrounding edema (if it exists) demonstrated on CT/MRI plus a 2.0-cm margin (this 2.0-cm margin-extended volume will be considered the initial planning target volume, or PTV1). The initial target volume will be treated to 46 Gy at 2Gy/fraction or 45-50.4 Gy at 1.8Gy/fraction. If no surrounding edema is present, the initial planning target volume (PTV1) should include the contrast-enhancing lesion (and should include the surgical resection cavity) plus a 2.5-cm margin. Please note that clinical judgment may be used to modify PTV1 to exclude sensitive structures such as the optic chiasm, non-cranial contents, or anatomic regions in the brain where natural barriers would likely preclude microscopic tumor extension, such as the cerebellum, the contralateral hemisphere, directly across from the tentorium cerebri, the ventricles, etc. After 46 Gy, the tumor volume (GTV2) for the conedown treatment should include the contrast-enhancing lesion (without edema) on the pre-surgery CT/MRI scan plus a 1.5-2-cm margin (PTV2). Treat to 14 Gy at 2Gy/fraction or 14.4-9.0 Gy at 1.8Gy/fraction to a total of 60.0 or 59.4Gy, respectively.

Dose is prescribed to the isodose line such that at least 95% of the target volume receives the prescribed dose.

The optic apparatus should be limited to a maximum of 54Gy and no more than 5% of the volume of the brainstem should receive >54 Gy.

Radiation will be delayed or interrupted if the platelet count is $< 20,000$. Radiation will not begin or resume until the platelet count is $\geq 20,000$. Hematologic toxicities should be rated on a scale of 0-5 as defined in the NCI Common Terminology Criteria for Adverse Events (CTCAE) version 5.0.

If radiotherapy has to be temporarily interrupted for technical or medical reasons unrelated to the temozolamide administration, then treatment with daily temozolamide should continue. If radiotherapy has to be permanently interrupted then treatment with daily temozolamide should stop.

18.2 Appendix B: Temozolomide Therapy during Radiation

TMZ should be administered continuously from day 1 of radiotherapy to the last day of radiation at a daily oral dose of 75 mg/m^2 for a maximum of 49 days. The drug will be administered orally 1 hour before each session of radiotherapy during weekdays (Monday through Friday). During weekends without radiotherapy (Saturday and Sunday), the drug will be taken in the morning. The dose will be determined using the body surface area (BSA) calculated at the beginning of the concomitant treatment. The BSA will be calculated from the height obtained at the pretreatment visit and the weight obtained at the visit immediately before the first day of treatment. Capsules of TMZ are available in 5, 20, 100, 140, 180 and 250 mg. The daily dose will be rounded to the nearest 5 mg. Patients will be instructed to swallow the capsules whole, in rapid succession, without chewing them. If vomiting occurs during the course of treatment, no re-dosing of the patient is allowed before the next scheduled dose. The capsules should be taken on an empty stomach, therefore a minimum of 2 hours after a meal and with no food ingestion for 1 hour after TMZ administration. Antiemetic prophylaxis is usually not required for the continuous daily dosing schedule. However, prophylaxis with a 5-HT3 antagonist is recommended prior to administration of the first few TMZ doses and should be administered orally 30 to 60 minutes before TMZ treatment.

No dose reduction should be made, but delay or discontinuation of TMZ administration should be decided weekly according to hematologic and non-hematologic AEs. If one or more of the following are observed:

- ANC $< 1.0 \times 10^9/\text{L}$
- Platelet count $< 75 \times 10^9/\text{L}$
- Grade 3 non-hematologic AE (except for alopecia, nausea and vomiting if controlled by maximal antiemetic therapy, and fatigue if controlled by pharmacologic or non-pharmacologic therapy)

then treatment with concomitant TMZ will be withheld until all of the following conditions are met:

- ANC $\geq 1.0 \times 10^9/\text{L}$
- Platelet count $\geq 75 \times 10^9/\text{L}$
- Grade ≤ 1 non-hematologic AE(except for alopecia, nausea and vomiting if controlled by maximal antiemetic therapy, and fatigue if controlled by pharmacologic or non-pharmacologic therapy)

In case of hematologic AE as defined above, a CBC should be performed at least twice weekly. In case of non-hematologic AE, the patient should be assessed at least weekly with relevant laboratory test(s). As soon as all of the above conditions are met, the administration of TMZ will resume at the same dose as used initially.

If one or more of the following are observed:

- ANC $< 0.5 \times 10^9/\text{L}$ (Grade 4)
- Platelet count $< 10 \times 10^9/\text{L}$ (Grade 4)
- Grade 3 or 4 non-hematologic AE (except for alopecia, nausea and vomiting if controlled by maximal antiemetic therapy, and fatigue if controlled by pharmacologic or non-pharmacologic therapy)

then treatment with concomitant TMZ should be **stopped**.

If the duration of radiotherapy exceeds 7 weeks, then concomitant treatment with TMZ should be stopped after 49 days of TMZ treatment. If the administration of TMZ has to be interrupted, the radiotherapy will proceed normally. Missed doses of TMZ will not be made up at the end of radiotherapy. The total number of days and total dose of TMZ will be recorded.

Table 1: Summary of TMZ Delay or Discontinuation during Concomitant Radiation Therapy AE

	Value	Grade	Action
ANC	≥ 0.5 and $< 1.0 \times 10^9/L$	2, 3	Delay TMZ until: 
 • ANC $\geq 1.0 \times 10^9/L$ • Plt $\geq 75 \times 10^9/L$ • Non-hem AE ≤ 1
Platelet count	≥ 10 and $< 75 \times 10^9/L$	2, 3	
Non-hematologic (except for alopecia, nausea/vomiting if controlled by maximal antiemetic therapy)	NA	3	
ANC	$< 0.5 \times 10^9/L$	4	
Platelet count	$< 10 \times 10^9/L$	4	Stop concomitant TMZ
Non-hematologic (except for alopecia, nausea/vomiting if controlled by maximal antiemetic therapy)	NA	4	

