1. Patients must have completed standard RT at the discretion of the treating Radiation Oncologist and concomitant TMZ therapy at a targeted dose of 75mg/m²/d for ≤ 49 days without significant toxicity that persisted over 4 weeks. Significant toxicity is defined as one or more of the following:
 - a. ANC $< 0.5 \times 10^9/L$ (Grade 4)
 - b. Platelet count $< 10 \times 10^9/L$ (Grade 4)
 - c. Grade 3 or 4 non-hematologic toxicity (except alopecia, nausea and vomiting unless the patient has failed maximal antiemetic therapy, and fatigue).
2. History & physical with neurologic examination within 14 days prior to initiation of adjuvant TMZ.
3. For patients receiving steroids, daily dose must be ≤ 4 mg.
4. CBC with differential obtained within 14 days prior to initiation of TMZ with adequate bone marrow function as defined below:
 - a. Absolute neutrophil count (ANC) $\geq 1500 \text{ cells/mm}^3$.

- b. Platelet count $\geq 100,000$ cells/mm³.
- c. Hemoglobin ≥ 10 g/dl. (The use of transfusion or other intervention to achieve Hgb ≥ 10 g/dl is acceptable.)

5. Adequate renal function within 14 days prior to initiation of adjuvant TMZ as defined below:

- a. BUN ≤ 25 mg/dl
- b. Creatinine ≤ 1.7 mg/dl

6. Adequate hepatic function within 14 days prior to initiation of adjuvant TMZ as defined below:

- a. Bilirubin ≤ 2.0 mg/dl
- b. ALT ≤ 5 times institutional upper limits of normal for age
- c. AST ≤ 5 times institutional upper limits of normal for age

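### Appendix B tells the clinician both to withhold and resume, and to stop, concomitant temozolomide for the same grade 3 non-hematologic adverse event

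*Combined protocol and SAP*

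**What the plan says.** Appendix B (section 18.2) allows no dose reduction of TMZ during radiotherapy. Delay or discontinuation is decided weekly from two lists and a summary table.

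- **Withhold list.** One trigger is "Grade 3 non-hematologic AE (except for alopecia, nausea and vomiting if controlled by maximal antiemetic therapy", with controlled fatigue also excepted. The action is "then treatment with concomitant TMZ will be withheld until all of the following conditions are met": ANC at least 1.0, platelets at least 75 (both × 10⁹/L) and any non-hematologic event at grade 1 or lower. After that, "the administration of TMZ will resume at the same dose as used initially".
- **Stop list.** The triggers are ANC below 0.5 and platelets below 10, both labelled grade 4, and "Grade 3 or 4 non-hematologic AE (except for alopecia, nausea and vomiting if controlled by maximal antiemetic therapy", again with controlled fatigue excepted. The action is to stop concomitant TMZ.
- **Table 1.** The row "Non-hematologic (except for alopecia, nausea/vomiting if controlled by maximal antiemetic therapy" appears twice: at grade 3 among the delay rows, and at grade 4 among the rows whose action is "Stop concomitant TMZ". Neither entry carries the fatigue exception.

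Section 8.1 (and the Synopsis) uses the same three thresholds as the stop list to define significant toxicity, including "Grade 3 or 4 non-hematologic toxicity (except alopecia, nausea and vomiting unless the patient has failed maximal antiemetic therapy, and fatigue". There the test is whether the toxicity persisted for more than 4 weeks, and it is applied before adjuvant TMZ.

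**The concern.** One event, a grade 3 non-hematologic adverse event outside the listed exceptions, attracts two different instructions. A clinician following the withhold list suspends TMZ and restarts it at full dose on recovery. A clinician following the stop list gives no more TMZ for the rest of radiotherapy. This is both a safety and a treatment question, and the text gives no order of precedence.

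Section 9.4 lets patients have chemoradiation with a local oncologist, so different teams could follow different lists.

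There is also a possible link to evaluability. Section 9.8 names patients who do not complete radiation with concomitant TMZ among those who may be replaced, and section 15.3.1 requires completed chemoradiation for the primary and secondary endpoints. No text says whether an early TMZ stop counts as non-completion, so this is a possibility and not a demonstrated effect.

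**Working it through.** No figure in the plan needs reproducing. The check sets the two lists and Table 1 side by side and asks what is left for delay once the stop list is applied. ANC and platelets are in × 10⁹/L.

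| Item | Withhold list | Stop list | Left for delay | Table 1 delay | Table 1 stop |
|---|---|---|---|---|---|
| ANC | <1.0 | <0.5 | 0.5 to <1.0 | ≥0.5 and <1.0 | <0.5 |
| Platelets | <75 | <10 | 10 to <75 | ≥10 and <75 | <10 |
| Non-hematologic | grade 3 | grade 3 or 4 | none | grade 3 | grade 4 |

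1. **Could the lists be escalating tiers, with the stricter rule overriding?** For ANC and platelets, yes. The stop threshold lies inside the withhold range, and the remainder is exactly the band that Table 1 prints for delay. For non-hematologic events, no. The withhold item is grade 3 alone and the stop item also covers grade 3. If the stop list always overrode, the non-hematologic withhold trigger could never operate.

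2. **Do the exceptions separate the two items?** No. Both except alopecia, controlled nausea and vomiting, and controlled fatigue. Neither adds a condition on recurrence, duration, relatedness or failure to recover.

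3. **Does Table 1 settle it?** It shows the probable intent but has no stated precedence. Of the appendix's three statements on a grade 3 event, two say delay (withhold list and Table 1) and one says stop. The cells of Table 1 are imperfectly aligned in the text available, but its grade column separates 3 from 4. The conflict stands on the two lists alone.

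4. **What do the adjuvant rules do?** Appendices C and D reduce the dose by one level at a first grade 3 non-hematologic event and stop at grade 4. They stop at grade 3 only if the same event recurs after a reduction or no lower dose level remains, and they state those conditions. This ladder agrees with Table 1.

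5. **What points the other way?** The significant-toxicity definition in section 8.1 has the same three thresholds as the stop list, including grade 3 or 4 for non-hematologic events. The stop wording may have been carried over from there, or it may be deliberate. The documents do not say which.

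6. **Does stopping concomitant TMZ bar adjuvant TMZ?** Not by itself. The section 8.1 test is toxicity that persisted for more than 4 weeks, not whether TMZ was stopped.

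**The case against.** The strongest reply accepts the overlap but treats it as a slip with little practical effect. Table 1 and the adjuvant ladder make the intended rule fairly clear, and the stop item is the outlier. Section 9.5 calls Appendix B a guideline and leaves chemotherapy to the treating neuro-oncologist under institutional practice. Section 13.5.12 says that TMZ is given as standard of care, with toxicity handled by standard clinical guidelines. Variation between teams is therefore already permitted. The rule is identical in all arms and acts before any vaccine, while section 15.3.1 counts survival from first vaccination. Recent entries in the amendment log mostly concern analysis and personnel, so a change may reach few new patients.

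Most of this stands, and it limits the weight. It does not remove the conflict. Table 1 reduces the ambiguity, but nothing says that it overrides the text. Clinical discretion does not tell a clinician which of two printed recommendations the guideline makes. The documents do not state that accrual has closed, so the timing argument is inference.

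The missing fatigue exception in Table 1 is a small separate item: both lists carry it, and the table is only a summary.

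**Conclusion.** The concern holds. Appendix B gives incompatible instructions for a grade 3 non-hematologic event during chemoradiation, and no text resolves them. The consequence is whether a recovered patient restarts TMZ at full dose or receives none for the rest of radiotherapy.

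The weight is minor to moderate: a correction worth considering, not a threat to the trial's inference. No effect on power, alpha, endpoints or the primary comparison is shown, and an effect on evaluability is only possible. The number of patients concerned cannot be given, because the documents report no rate of grade 3 non-hematologic events during chemoradiation.

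The finding rests only on the wording of the two lists. The view that grade 4 is the intended stop threshold rests on Table 1, on the grade 4 labels of the other two stop items and on Appendices C and D. It needs clinical confirmation.

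**What to change.** In the Appendix B stop list, limit the non-hematologic item to grade 4, so that it matches Table 1 and the other two stop items. The clinical lead should confirm this direction first, because of the shared wording with the significant-toxicity definition in section 8.1 and the Synopsis.

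If stopping at grade 3 is what is wanted, remove grade 3 from the withhold list and from the delay rows of Table 1, and show grades 3 and 4 together in the stop row.

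In either case, add the controlled-fatigue exception to the non-hematologic rows of Table 1.

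The cost is a few words in the appendix and its table, with no change to sample size, alpha, endpoints or data collection.

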18.3 Appendix C: Temozolomide Therapy after Radiation

TMZ will be administered orally once per day for 21 consecutive days (days 1-21) of a 35 (+/- 7) day cycle. The starting dose for the first cycle will be 75 mg/m²/day, with a single dose escalation to 100 mg/m²/day in subsequent cycles if no adverse events \geq grade 2 are noted.

Twelve cycles of TMZ may be given if the patient demonstrates continued improvement on MR scan, decreased corticosteroid requirement, improvement in performance status, or improvement in neurologic function.

Dosing Modifications

Dosing is based on adverse events (AEs) during the prior treatment cycle. If multiple AEs are seen, the dose administered should be based on the dose reduction required for the most severe grade of any single AE as shown in Table 2.

Table 2: Dosing Modification Schedule for TMZ per RTOG 0525 Regimen

Dose Level	Dose, mg/m ² /day x 21 days	Remarks
-2	35	Reduction if prior AE
-1	50	Reduction if prior AE
0	75	Starting dose for cycle 1, increase to 100 mg/m ² for cycle 2 and beyond if no hematologic toxicity \geq grade 2 and non-hematologic toxicity $>$ grade 2
+1	100	Highest possible dose level (adjuvant)

First cycle

TMZ will be started at a dose of 75 mg/m²/day.

Second cycle

The dose of TMZ will be determined according to (1) non-hematologic AE during the preceding treatment cycle, as well as (2) the nadir (lowest/worst) ANC and platelet counts.

Cycles 3-12

Any dose reductions of TMZ will be determined according to (1) non-hematologic AE during the preceding cycle, as well as (2) the nadir (lowest/worst) ANC and platelet counts. No dose escalation should be attempted. The same dose reductions as for the second cycle should be applied. If the dose was reduced or delayed for adverse events, there will be no dose escalation.

Delay

On day 1 of each cycle (within the prior 72 hours), ANC \geq 1 x 10/L, platelet count \geq 100 x 10/L and all grade 3 or 4 non-hematologic AEs (except for alopecia, nausea, and vomiting if controlled by maximal antiemetic therapy) must have resolved (to grade \leq 1).

If AEs persist, treatment should be delayed by 1 week for up to 4 consecutive weeks. If, after 4 weeks of delay, all AEs have still not resolved: then any further adjuvant treatment with TMZ should be stopped.

Dose escalation

If, during the first cycle, all non-hematologic AEs observed were grade ≤ 2 (except for alopecia, nausea and vomiting if controlled by maximal antiemetic therapy) and with platelets $\geq 100 \times 10^9/L$ and ANC $\geq 1 \times 10^9/L$: then the TMZ dose should be escalated to dose level +1 and this dose should be used as the maintenance dose for subsequent cycles. If treatment after cycle 1 has to be delayed by any length of time because of ongoing hematologic AEs ≥ 2 and/or non-hematologic AEs of grade > 2 (except for alopecia, nausea and vomiting if controlled by maximal antiemetic therapy), then no escalation is possible. If the dose was not escalated at cycle 2, then the dose should not be escalated in further cycles (3-12).

Dose reductions

If any non-hematologic AE observed was grade > 2 (except for alopecia, nausea and vomiting if controlled by maximal antiemetic therapy) and/or if platelets $< 100 \times 10^9/L$ and/or ANC $< 1 \times 10^9/L$, then the dose should be reduced by one dose level. For patients who would require dose reductions to a dose level $< 35 \text{ mg/m}^2/\text{day}$ (dose level -2), TMZ will be stopped. Also, if any of the same non-hematologic grade 3 AE recurs (except for alopecia, nausea and vomiting if controlled by maximal antiemetic therapy) after reduction for that AE, then TMZ will be stopped. If any treatment-related non-hematologic AE observed was grade 4 (except for alopecia, nausea and vomiting if controlled by maximal antiemetic therapy) then adjuvant TMZ treatment should be stopped. Please see Tables 3-6 for a summary of dose modification or discontinuation.

The reason(s) for dose reduction and/or delay must be documented in the CRF.

Table 3: Summary of Dose Modification or Discontinuation During Post-Radiation Temozolomide Worst Non-Hematologic AE (except for alopecia, nausea and vomiting if controlled by maximal antiemetic therapy) During the Previous Cycles

Grade	Dose Modification
0-2	No dose modifications for non-hematologic AEs. Dose escalations (only for cycle 2) or reductions based on ANC and platelet counts are applicable.
3	Reduce by one dose level (except for alopecia, nausea and vomiting if controlled by maximal antiemetic therapy). Dose modifications (escalations or reductions) based on ANC and platelet counts are not applicable. No further escalation is possible. If the same non-hematologic grade 3 AE recurs (except for alopecia, nausea and vomiting if controlled by maximal antiemetic therapy) after reduction for that AE, then stop.
4	Stop (except for alopecia, nausea and vomiting if controlled by maximal antiemetic therapy). Dose modifications (escalations or reductions) based on ANC and platelet counts are not applicable.

Table 4: Worst Treatment-Related Hematologic AE during the Previous Cycles

Worst AE		Platelets	
		$\geq 100 \times 10^9/L$	$< 100 \times 10^9/L$
ANC	$\geq 1.5 \times 10^9/L$	Dose unchanged	Reduce by 1 dose level
	$\geq 1 & < 1.5 \times 10^9/L$	Dose unchanged	Reduce by 1 dose level
	$< 1 \times 10^9/L$	Reduce by 1 dose level	Reduce by 1 dose level

Note: A complete blood count will be performed prior to each vaccine and if clinically indicated on days 7, 14, 21 and 28 (+/- 72 hours) after the first daily dose of each adjuvant treatment cycle.

Table 5: Hematological AE on Day 1 of Each Cycle (within the prior 72 hours before Day 1

AE	Delay
ANC < $1 \times 10^9/L$ and/or Platelet count < $100 \times 10^9/L$	Delay up to 4 weeks until all resolved. If unresolved after 4 weeks then stop. If resolved, dose delay/reductions based on hematologic and non-hematologic AEs are applicable.

Table 6: Non-Hematologic AE (except for alopecia, nausea and vomiting if controlled by maximal antiemetic therapy) on the day 1 of Each Cycle (within the prior 72 hours)

Grade	Delay
2-3	Delay up to 4 weeks until all resolved (to grade ≤ 1). If unresolved after 4 weeks then stop. If resolved, dose delay/reductions based on hematologic and non-hematologic AEs are applicable.
4	Stop (except for alopecia, nausea and vomiting if controlled by maximal antiemetic therapy).

